8.2.1.2 Success Criteria for Evaluation of Primary Efficacy Objective

Vaccine Efficacy (VE) and its CI will be calculated for the RT-PCR-confirmed or culture confirmed influenza A and B disease presenting as influenza like illness (ILI).

The primary efficacy objective is achieved if the lower limit (LL) of the two-sided 95% confidence interval (CI) of the estimator of absolute vaccine efficacy of QIVc versus non-influenza comparator vaccine calculated from cases of all strains in subjects ≥ 2 years to < 18 years of age is greater than 20%.

In case an interim analysis will be performed the 95% CI will be adjusted accordingly; further details will be specified in the SAP.

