8.4.2.2.4 Statistical Methods for Primary and Co-Primary Efficacy Objectives

For each of the age groups (≥ 2 to < 18 and ≥ 3 to < 18 years), the HR³ and the related 95% CI of HR, for onset of first RT-PCR or culture confirmed influenza will be estimated by a proportional hazards regression model with treatment effect as a fixed effect and stratifying covariates as random effect:

$h_i(t|X) = h_0(t) \exp(\beta^T X + b^T Z)$, with t denoting time to the influenza, β is the effect of treatment group indicated by X , b is random effect (assumed as a multivariable random gaussian variable with zero mean and diagonal covariance matrix), Z is random effect covariate (reflecting randomization strata, see [SAP for](#) further discussion of the covariates utilized).

Subjects that did not experience ILI during observation period and subjects that dropped out from the study during observational period will be censored (right-censoring). The estimate of the hazard ratio, the respective estimate for absolute VE and the pertaining two-sided CIs will be calculated based on this model. If the study continues over several seasons, estimates will be also adjusted for the factor season (s). In case of one or two (interim) analyses, confidence levels at each stage will be adjusted to provide 95% overall coverage.

For each of the age groups (≥ 2 to < 18 and ≥ 3 to < 18 years), estimates for hazard ratio in Cox Proportional hazard (PH) model will be calculated using Maximum Likelihood (ML) method. In case of problems with convergence (algorithm does not converge or converges to infinite estimates) penalized ML approach will be used ([Heinze and Schemper](#)).

Vaccine efficacy $VE = 1 - HR$, that is, $1 - \exp(\hat{\beta})$

with $\hat{\beta}$ with $100(1 - \alpha)$ percent confidence interval as:

³ Formula: $VE=1-HR$

$[1 - \exp(+Z(\text{s.e.}(\hat{\beta}))); 1 - \exp(\hat{\beta} - Z(\text{s.e.}(\hat{\beta})))]$. Z is the 100(1- α) percent point of the standard normal distribution, and s.e. denotes the standard error of $\hat{\beta}$.

The hazard ratio is the predicted ratio of cases of Influenza A and or B disease in subjects receiving QIVc and non-influenza vaccine comparator within each of the strata of interest. The term $\hat{\beta}_g$ is the estimate of treatment effect (or regression coefficient) between QIVc and non-influenza vaccine comparator within each of the stratum.

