In case the DMC states that the observed data provides already the full information level needed for the final test decision, then the final analysis can be done on full alpha level (2.5 % 1-sided) and no further enrollment is needed. However if the decision of the group-sequential test is to continue the study then it is on the DMC to determine the number of subjects needed to be enrolled. The monitoring committee should not be influenced by the individual results of the vaccine groups observed at an interim analysis stage when planning further subjects' accrual or the times of future analysis. Only the overall number of cases is allowed to be used for further planning. The following formula for determination of sample sizes for further enrollment may be used:

$$N_{\text{total}} = (C_{\text{planned}} - C_{\text{observed}}) / [(ER_{\text{QIVc}} + ER_{\text{comp}})/2],$$

where N_{total} denotes the total number of subjects needed for further enrollment, C_{planned} is the overall number of cases needed for the test, i.e. 381 cases, C_{observed} are the at that stage observed number of cases overall, and ER are the respective event rates assumed for each group, i.e., 8,0% for non-influenza comparator group and 4,0% for QIVc. A consideration of early dropout and uncertainty about assumed parameters will be accounted for number of enrolled subjects. The method of stopping rules given above is statistical and should be completed by clinical and strategic stopping rules that allow the DMC to make a decision on a broader picture of the data which includes safety endpoints and the other endpoints of the study.

Stopping rules for futility and efficacy and any additional details regarding the interim analysis will be specified in the DMC Charter and in the SAP.

For the interim analyses, if needed, a restricted unblinding will be done, i.e., only DMC members and unblinded CRO employees responsible for the analyses will receive access to the randomization codes and unblinded data for the purpose of preparing the interim analyses (further information on handling of the blinding for the interim analyses can be found in section 3.3). The results of the interim analyses are only for DMC purposes and will not be reported in the Clinical Study Report (CSR).

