11. EFFICACY ANALYSIS

11.1 Primary Efficacy Objectives Analysis

Efficacy will be evaluated in all subjects in relation to cases occurring >14 days after last vaccination and until the end of study or the end of the influenza season, whichever is longer, using the following null (H_0) and alternative (H_1) hypotheses:

$$H_0: 1 - HR = VE \leq 0.2 \quad \text{versus} \quad H_1: 1 - HR = VE > 0.2,$$

where HR is a hazard ratio of QIVc versus non-influenza comparator and VE is vaccine efficacy. The primary objective will be achieved if the lower limit of the two-sided confidence interval of VE estimate, with at least 95% coverage in a multiple sequential hypothesis testing, exceeds 0.2 in subjects ≥ 2 years to <18 years of age.

The co-primary objective will be achieved if the lower limit of the two-sided confidence interval of VE estimate, with at least 95% coverage in a multiple sequential hypothesis testing, exceeds 0.3 in subjects ≥ 3 years to <18 years of age.

The co-primary objective will only be demonstrated in case of successful demonstration of the primary efficacy objective (i.e. in hierarchical testing procedure, only after demonstration of absolute vaccine efficacy of QIVc in subjects ≥ 2 years to <18 years of age).

In case an interim analysis will be performed the 95% CI will be adjusted accordingly. If an interim analysis is performed and the trial doesn't stop, then all the subsequent analysis will be tested at a reduced alpha level, i.e. what's left from the interim analysis. The confidence interval will be higher than 95% instead of 95% for the final analysis.

(Co-)Primary vaccine efficacy analyses will be based on the Efficacy FAS, and repeated on the Efficacy PPS.

For each of the age groups (≥ 2 to <18 and ≥ 3 to <18 years), the HR² and the related 95% CI of HR, for onset of first RT-PCR or culture confirmed influenza will be estimated by a proportional hazards regression model with treatment effect as a fixed effect and stratifying covariates as random effect:

$h_i(t|X) = h_0(t) \exp(\beta^T X + b^T Z)$, with t denoting time to the influenza, β is the effect of treatment group indicated by X , b is random effect (assumed as a multivariable random gaussian variable with zero mean and diagonal covariance matrix), Z is random effect covariate (reflecting randomization strata, see [Section 8.1](#) for further discussion of the covariates utilized).

² Formula: $VE=1-HR$

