Subjects that did not experience ILI during observation period and subjects that dropped out from the study during observational period will be censored (right-censoring). The estimate of the hazard ratio, the respective estimate for absolute VE and the pertaining two-sided CIs will be calculated based on this model. If the study continues over several seasons, estimates will be also adjusted for the factor season (s). In case of one or two (interim) analyses, confidence levels at each stage will be adjusted, as discussed in section 14.1, to provide 95% overall coverage.

For each of the age groups (≥ 2 to <18 and ≥ 3 to <18 years), estimates for hazard ratio in Cox Proportional hazard (PH) model will be calculated using Maximum Likelihood (ML) method. In case of problems with convergence (algorithm does not converge or converges to infinite estimates) penalized ML approach will be used (Heinze and Schemper).

Vaccine efficacy $VE = 1 - HR$, that is, $1 - \exp(\hat{\beta})$

with $\hat{\beta}$ with $100(1 - \alpha)$ percent confidence interval as:

$[1 - \exp(+Z(s.e.(\hat{\beta}))); 1 - \exp(\hat{\beta} - Z(s.e.(\hat{\beta})))]$. Z is the $100(1 - \alpha)$ percent point of the standard normal distribution, and s.e. denotes the standard error of β

Subjects that did not experience ILI during observation period and subjects that dropped out from the study during observational period will be censored (right-censoring).

The hazard ratio is the predicted ratio of cases of Influenza A and or B disease in subjects receiving QIVc and non-influenza vaccine comparator within each of the strata of interest. The term β_g is the estimate of treatment effect (or regression coefficient) between QIVc and non-influenza vaccine comparator within each of the stratum.

The estimate of the hazard ratio, the respective estimate for absolute VE and pertaining two-sided 95% CIs will be calculated based on this model. If the study continues over several seasons, estimates will be also adjusted for the factor season (s). Factor country might be added to the model if appropriate. In case of more than one interim analysis confidence level for the estimates at the final stage will be adjusted.

Primary analysis will take into account only first ILI episode for a subject.

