- If the number of RT-PCR confirmed influenza cases is greater or equal to 381 (targeted number of cases to be able to evaluate the co-primary objective) and subjects have been enrolled over at least three seasons the study will be unblinded and the final analysis will be performed by the sponsor. If the trial proceeds to the final analysis (upon reaching 381 cases) the boundaries for acceptance or rejection are identical to the assumed type 1 and type 2 errors for the overall design, and the trial stops to either reject or not reject the null hypothesis of the primary objective.

That is, the primary objective, i.e. VE against RT-PCR or culture confirmed influenza A and or B will be assess the one-sided 0.025 alpha level.

In case the DMC states that the observed data provides already the full information level needed for the final test decision, then the final analysis can be done on full alpha level of (2.5 % 1-sided) and no further enrollment is needed. If, however, the decision of the group-sequential test is to continue the study then it is on the DMC to determine the number of subjects needed to be enrolled. The DMC should not be influenced by the individual results of the vaccine groups observed at an interim analysis stage when planning further subjects' accrual or the times of future analysis. Only the overall number of cases is allowed to be used for further planning. The following formula for determination of sample sizes for further enrollment may be used:

$$N_{\text{total}} = (C_{\text{planned}} - C_{\text{observed}}) / [(ER_{\text{QIVc}} + ER_{\text{comp}})/2],$$

where N_{total} denotes the total number of subjects needed for further enrollment, C_{planned} is the overall number of cases needed for the test, i.e. 381 cases, C_{observed} are the at that stage observed number of cases overall, and ER are the respective event rates assumed for each group, i.e., 8.0% for non-influenza comparator group and 4.0% for QIVc.

For the analysis of for efficacy, an error-spending function will be applied to provide statistical stopping rules for efficacy (α -boundaries) for the first interim analysis and second interim analysis, if necessary, based on the information accumulated until that specific interim stage, i.e. based on the accumulated variance of the parameter of interest.

These boundaries will be calculated on a p-value see:

<https://support.sas.com/documentation/onlinedoc/stat/131/seqdesign.pdf>

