At each interim stage, α -boundaries, forming the adjusted probabilities for the type 1 error, are calculated using error-spending function and if the p-value for the test of primary objective is lower than the respective α -boundary the trial stops for efficacy at this stage.

In other words the trial stops early for efficacy if data collected at this stage allows to demonstrate both primary and co-primary efficacy objectives (reject null-hypothesis). Further guided by efficacy estimates of QIVc described in secondary efficacy objective 4 (prevention of PCR confirmed influenza antigenic matched to the strains selected for the seasonal vaccine). Otherwise, the trial continues to the next stage and more subjects will be enrolled.

The cumulative O'Brien-Fleming type error-spending-function ([Lan and DeMets, 1983](#), option ERRFUNCOBF in SAS[®] PROC SEQDESIGN) will be used for both α - and β -boundaries; the error-spending function is defined as:

$$E(t; a) = \begin{cases} 1 & \text{if } t \geq 1 \\ \frac{1}{a} 2 (1 - \Phi(\frac{z(1-a/2)}{\sqrt{t}})) & \text{if } 0 < t < 1 \\ 0 & \text{otherwise} \end{cases}$$

where a equals α for α spending function and β for beta spending function, and where t is the information fraction.

If the trial proceeds to the final analysis, the boundary for rejection of null hypothesis is identical to the type 1 error (that is as the 0.025 one-sided alpha level) with power specified for the overall design, and the trial stops to either reject or not reject the null hypothesis of the primary objective.

Additional interim analyses may be requested at a future date (by the DMC), particularly if the first interim analysis is conducted soon after 191 cases of influenza have been reported. In this case, the DMC may request that a second interim analysis be conducted to allow for greater accuracy to determine if the trial should stop or continue.

Any modifications of a trial design (i.e. introducing additional interim analysis stage) and calculations of number of subjects to be additionally enrolled will be based on the assumptions as defined in the protocol Section 8.6, and will not be influenced by the results of an interim analysis.

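### The VE confidence-interval formula pairs a two-sided 100(1 − α)% interval with the 100(1 − α) normal percentile instead of the 100(1 − α/2) percentile, and leaves α without a value

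*SAP*

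**What the plan says.** SAP 11.1 estimates VE as 1 − exp(β̂) from the Cox model and gives its 100(1 − α) "percent confidence interval as" a pair of limits with Z times the standard error on either side of the estimate. Z is then the 100(1 − α) "percent point of the standard normal distribution, and s.e. denotes the standard error of" β. Protocol 8.4.2.2.4 has the same formula, with Z again the 100(1 − α) "percent point of the standard normal distribution". Neither section assigns α a value, although both speak of 95% intervals around the formula.

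The level is fixed elsewhere:

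- Protocol 8.2.1.2: "The primary efficacy objective is achieved if the lower limit (LL) of the two-sided 95% confidence interval (CI") for VE exceeds 20%. Protocol 8.2.1.3 has the parallel rule for the co-primary at 30%.
- SAP 11.1, on the success rule: a two-sided interval "with at least 95% coverage in a multiple sequential hypothesis testing".
- SAP 14.1: the primary objective "will be assess the one-sided 0.025 alpha level", and the final boundary is described as type 1 error, "that is as the 0.025 one-sided alpha level".
- Protocol 8.6: if full information has been reached, "then the final analysis can be done on full alpha level (2.5 % 1-sided").

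**The concern.** The lower limit of this interval decides both confirmatory objectives (VE above 20% in ages 2 to <18, above 30% in ages 3 to <18). It is also the only explicit interval formula that either document gives for the Cox-based VE.

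Put on both sides of an estimate, the 100(1 − α) normal point leaves α in each tail, so the interval covers 100(1 − 2α)% and not the labelled 100(1 − α)%. A programmer who takes α = 0.05 to obtain the 95% label, and then codes Z as written, produces a 90% interval and a confirmatory test at one-sided 5%. The risk is greater because the plan expects confidence levels to change when an interim analysis is run, so someone must turn a stage-specific α into a Z value from a line that does not say whether α is one-sided or two-sided.

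**Working it through.** **Inputs.** Margins VE 20% and 30% (HR₀ 0.80 and 0.70), assumed VE 45% and 50% (HR₁ 0.55 and 0.50), 298 and 381 events, about 90% power, 1:1 allocation: SAP 5 and 11.1, Protocol 8.5. One-sided α of 2.5%: Protocol 8.6, SAP 14.1.

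**1. Which Z does the design use?** Schoenfeld events against a shifted null: D = 4(Z + 1.2816)² / [ln(HR₁/HR₀)]².

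| | HR₁/HR₀ | [ln]² | Z = 1.960 | Z = 1.645 | Plan |
|---|---|---|---|---|---|
| Primary | 0.55/0.80 = 0.6875 | 0.1404 | 4 × 10.508/0.1404 ≈ 300 | 4 × 8.565/0.1404 ≈ 244 | 298 |
| Co-primary | 0.50/0.70 = 0.7143 | 0.1132 | 4 × 10.508/0.1132 ≈ 372 | 4 × 8.565/0.1132 ≈ 303 | 381 |

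With Z = 1.960 the plan's counts reproduce within 3%; with 1.645 they do not. The sample size therefore rests on the two-sided 95% rule.

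**2. What does the printed definition imply?** Coverage of β̂ ± z(1 − α) × s.e. is 2(1 − α) − 1 = 1 − 2α.

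| α taken as | Z as defined | Label 100(1 − α)% | Actual coverage | One-sided error |
|---|---|---|---|---|
| 0.05 (from the 95% wording) | 1.645 | 95% | 90% | 5% |
| 0.025 (one-sided α in Protocol 8.6, SAP 14.1) | 1.960 | 97.5% | 95% | 2.5% |

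The first row has the right label and the wrong limit; the second has the right limit and the wrong label.

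**3. Size if α = 0.05 is programmed.** Approximate the hazard ratio by the case ratio, single look, no strata: β̂ = ln(x/(D − x)) and s.e. = √(1/x + 1/(D − x)), with x the QIVc cases.

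- At the assumed VE of 50%, 381 events split 127 v 254, so s.e. = √(1/127 + 1/254) = 0.1087. The lower limit is 1 − 0.5 × exp(1.645 × 0.1087) = 40.2%, or 1 − 0.5 × exp(1.96 × 0.1087) = 38.1%.
- The largest x for which the Wald lower limit still clears the margin, with the binomial tail P(X ≤ x) at the margin, where p₀ = HR₀/(1 + HR₀):

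| | p₀ | Z = 1.645 | Tail | Z = 1.960 | Tail |
|---|---|---|---|---|---|
| Co-primary, 381 events | 0.7/1.7 | 141 (VE 41.3%) | 5.4% | 138 (VE 43.2%) | 2.7% |
| Primary, 298 events | 0.8/1.8 | 118 | 5.2% | 115 | 2.4% |

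The cut-offs come from the Wald limit, as in the plan's formula, and only the tails are exact. For the co-primary, an exact conditional test would allow 140 cases (4.3%) and 137 cases (2.1%).

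**The case against.** A reader might infer that the plan tests its confirmatory objectives at one-sided 5%. The documents do not support that. Every statement of the rule itself is two-sided 95% or one-sided 2.5%, the event counts reproduce only with 1.96, and where the α of the efficacy test is given a number it is 0.025 one-sided. With that α the formula returns 1.96 and the correct limit; a wrong label does not move the limit that decides success. All of this stands, and it makes the inflation conditional.

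A second objection is that the formula may not be the operative calculation. SAP 14.1 allows PROC SEQTEST to supply confidence limits after the trial stops, and the protocol says repeated and final intervals can be retrieved by the group-sequential method. Both statements are permissive, however, and interim analyses are optional in the SAP. A single-look analysis could rest on the SAP 11.1 formula alone.

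A third is that the line is too damaged to read literally. In the text available for this review, the lower limit in both documents lacks β̂. Taken at face value it would always be below zero and could never pass. That may be a loss in reading the PDF, so nothing here rests on it. The sentence defining Z is intact and the same in both documents, so that explanation does not extend to the percentile.

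**Conclusion.** The percentile is mis-stated in both documents, and no choice of α repairs label and percentile together. This is a notation error in the formula that implements the success rule, with a possible programming consequence; it is not a success rule set at the wrong level.

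The consequence arises only if the line is coded as written with α = 0.05. Coverage would then be 90%, the one-sided error about 5% against the intended 2.5%, and three more QIVc cases would be tolerated at each target event count (141 v 138 of 381; 118 v 115 of 298). The case figures assume 1:1 allocation, a single look, and a hazard ratio close to the case ratio without strata. If α is taken as the one-sided 0.025, there is no inflation, only a mislabelled interval.

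It should be corrected because the same line decides both confirmatory claims and the intended value is not in doubt.

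**What to change.** In SAP 11.1 and Protocol 8.4.2.2.4, replace the interval with

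[1 − exp(β̂ + z(1 − α/2) × s.e.(β̂)); 1 − exp(β̂ − z(1 − α/2) × s.e.(β̂))],

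where z(1 − α/2) is the 100(1 − α/2) percent point of the standard normal and α is the two-sided level available at that stage: 0.05, so Z = 1.96, if no interim analysis was run, and otherwise the stage-specific level. Check the source files to confirm that β̂ is present in the lower limit.

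The cost is one formula line and its definition in each document. The design, event targets and success criteria do not change.

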sBLA	Supplement Biologics License Application
SC	Seroconversion
SDA	Source Data Agreement
SH	Southern Hemisphere
SOC	System Organ Class
SOP	Standard Operating Procedure
TIV	Trivalent Influenza Vaccine
VRBPAC	Vaccines and Related Biological Products Advisory Committee
VSAE	Vaccine Serious Adverse Events
WHO	World Health Organization

DEFINITIONS

End of influenza season: The end of the influenza season will be defined as the end of June for Northern Hemisphere (NH) influenza seasons and end of December for Southern Hemisphere (SH) influenza seasons. For tropical countries, with no typical NH or SH influenza season, the season is defined by the use of the strains in the vaccine formulation (i.e. strains as recommended for the NH or the SH influenza season) and the timing of vaccination.

End of study: Evaluation of the primary and secondary efficacy objectives requires the testing of biological samples from the study subjects, which can only be completed after all samples are collected. Nasopharyngeal swabs may be collected up to end of influenza season. For the purpose of this protocol, end of study is defined as the completion of the testing of such biological samples, to be achieved no later than 8 months after LSLV.

Influenza case: An ILI associated with RT-PCR or culture confirmed influenza.

Influenza-like illness (ILI) onset: The first day on which a subject fulfils the criteria for protocol-defined ILI.

Medically-attended Adverse Event: Defined as symptoms or illnesses requiring hospitalization, or emergency room visit, or visit to/by a health care provider.

Study definition of Influenza-like illness (ILI): Fever of $\geq 37.8^{\circ}\text{C}$ (100°F) and at least one of the following: cough, sore throat, nasal congestion, or rhinorrhea.

Qualified healthcare professional: Any licensed health care professional who is permitted by institutional policy to perform clinical interventions and assessments such as physical examinations and who is identified within the Study Staff Signature Log.

Trained healthcare professional: Any health care professional who is permitted by institutional policy and trained to perform delegated tasks and who is identified within the Study Staff Signature Log.

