2.1.2 Primary and Co-Primary Endpoint

The primary and co-primary efficacy endpoint is the time from the last study vaccination to the onset of the first occurrence confirmed influenza by either RT-PCR-confirmed or culture-confirmed, due to any influenza Type A or B strain regardless of antigenic match to the strains selected for the seasonal vaccine, occurring > 14 days after the last vaccination and until the end of the influenza season.

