After randomization, all subjects will receive a dose of 0.5 mL of study vaccine to which they were assigned (QIVc or non-influenza comparator vaccine) on Day 1, administered intramuscularly in the deltoid muscle, preferably of the non-dominant arm. For those subjects who are “not previously vaccinated” a second administration will follow on Day 29, as presented below:

Table 3-2: Vaccination Schedule

Subjects	QIVc Group	Comparator Group
“previously vaccinated” ≥ 2 years to < 9 years of age, and ≥ 9 years to < 18 years of age	Day 1: QIVc	Day 1: Men ACWY
“not previously vaccinated” ≥ 2 years to < 9 years of age	Day 1: QIVc Day 29: QIVc	Day 1: Men ACWY Day 29: Saline

To maintain the observer-blind design of the study, the roles and responsibilities of “blinded” and “unblinded” team members will be defined. After vaccination, safety assessments and study related procedures and monitoring thereof must be performed by “blinded” team members.

This study is planned for at least three influenza seasons. Laboratory confirmed influenza cases will be reviewed on a regular basis (blinded review). If decided by the Sponsor, and after observing at least 50% of planned events meeting the co-primary endpoint, interim analyses for efficacy may be performed for evaluation by a DMC.

Study Definition of Influenza-Like-Illness and Influenza Case

An Influenza Like Illness (ILI) Case is defined as follows: The Centers for Disease Control and Prevention (CDC) criteria ILI is modified for young children for the purposes of this study to include additional symptoms): fever of $\geq 100.0^{\circ}\text{F}$ / $\geq 37.8^{\circ}\text{C}$ along with any of the following: cough, sore throat, nasal congestion, or rhinorrhea.

The ILI onset day is defined as the first day that the subject meets the primary protocol defined ILI.

The ILI end date is defined as the date the last symptom resolves.

A new ILI episode will only be taken into account after resolution of the previous one, as judged by the investigator (suggested interval between two ILI episodes is 14 symptom free days).

A detailed schedule and listing of procedures are shown in the Time and Events Tables 3-7 (see [protocol synopsis](#)).

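### SAP 11.1 limits the primary analysis to the first ILI episode, while the endpoint and model use the first confirmed influenza; read literally, a confirmed case after an unconfirmed ILI is lost

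*SAP*

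**What the plan says.** SAP 11.1 closes its description of the model with the event rule "Primary analysis will take into account only first ILI episode for a subject".

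Other places set the event differently:

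- SAP 2.1.2 defines the endpoint as time to "the onset of the first occurrence confirmed influenza by either RT-PCR-confirmed or culture-confirmed".
- SAP 11.1 itself estimates the hazard ratio "for onset of first RT-PCR or culture confirmed influenza will be estimated by a proportional hazards regression model", and opens with "Efficacy will be evaluated in all subjects in relation to cases occurring >14 days after last vaccination".
- The Definitions section of the protocol describes an influenza case as "An ILI associated with RT-PCR or culture confirmed influenza".

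SAP 3 defines ILI as fever plus at least one respiratory symptom, with no laboratory result. It also provides for repeats: "A new ILI episode will only be taken into account after resolution of the previous one".

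The censoring sentence in SAP 11.1, which appears twice, reads "Subjects that did not experience ILI during observation period and subjects that dropped out from the study during observational period will be censored". Protocol 8.4.2.2.4 has the same opening, "Subjects that did not experience ILI during observation period". The first-ILI sentence does not appear in that protocol section.

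**The concern.** A first ILI episode and a first confirmed influenza are different events. A child can have a febrile respiratory illness that tests negative, or is never swabbed, and confirmed influenza later in the same season. Surveillance is built for this: the protocol synopsis and Protocol 5.4.1 have a new ILI booklet handed out at the swab visit. Under the endpoint that child is a case. Under the literal first-ILI rule the child's only admissible episode is the unconfirmed one, and the later case is not counted.

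This sentence is the stated event rule for both confirmatory analyses. A programmer who follows the SAP's own definition of ILI has textual support for the literal reading: SAP 3 announces definitions of both ILI and influenza case under one heading but then defines only ILI. At stake are events, and therefore co-primary power or study duration.

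**Working it through.** **1. The design figure.** Inputs from SAP 5: null VE 30% (HR 0.7), assumed VE 50% (HR 0.5), two-sided 5%, about 90% power, 381 events; 1:1 allocation from SAP 4.1. Schoenfeld's formula gives

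D = 4 × (1.96 + 1.2816)² / [ln(0.7/0.5)]² = 42.03 / 0.1132 = 371.3, so 372.

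Freedman's formula gives 379. The stated 381 is reproduced within 2.4%. With an 8% attack rate in the comparator group and 4% under QIVc, the mean is 6%, and 381 / 0.06 = 6,350 evaluable subjects, as stated. These figures already count confirmed cases.

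**2. Which cases are lost.** Let q be the share of confirmed in-window cases preceded by an unconfirmed in-window ILI. The documents give no rate of non-influenza ILI, so q is an assumption and is shown as a range.

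**3. Power if monitoring counts all confirmed cases but the analysis drops some.** Power = Φ( ln(0.7/0.5) × √D / 2 − 1.96 ), without interim adjustment. The last column is 381 / [0.06 × (1 − q)].

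| Assumed q | Analysed events, 381 × (1 − q) | Co-primary power | Evaluable subjects needed to keep 381 countable events |
|---|---|---|---|
| 0% | 381 | 90.7% | 6,350 |
| 5% | 362 | 89.3% | 6,685 |
| 10% | 343 | 87.6% | 7,056 |
| 20% | 305 | 83.6% | 7,938 |
| 30% | 267 | 78.5% | 9,072 |

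**4. Is that mismatch possible?** The trigger for the final analysis in SAP 14.1 counts RT-PCR-confirmed cases and carries no first-ILI limit, so as written the monitored and analysed counts could differ. The trigger also requires enrolment over at least three seasons, so the count may pass 381 and absorb some loss. At q = 10%, 381 / 0.9 = 423.3, so 424 confirmed cases would leave 381 for analysis.

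**5. Effect on VE.** Simulation under assumptions that are not in the documents: constant hazards, 4,000,000 subjects per arm, cumulative influenza 8% and 4%, and independent other ILI equally frequent in both arms. The true VE on the hazard scale is 1 − ln(0.96)/ln(0.92) = 0.510.

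| Other ILI per arm | Cases lost, comparator / QIVc | VE, all cases | VE, follow-up ends at first ILI | VE, follow-up continues, case not counted |
|---|---|---|---|---|
| 10% | 5.0% / 5.1% | 0.508 | 0.508 | 0.508 |
| 20% | 10.2% / 10.1% | 0.508 | 0.508 | 0.507 |
| 30% | 15.7% / 15.8% | 0.510 | 0.510 | 0.510 |
| 40% | 21.4% / 21.5% | 0.510 | 0.510 | 0.509 |

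Both arms lose nearly the same share of cases, and VE does not move.

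**The case against.** The strongest reply is that the sentence is shorthand. The endpoint and the model fix the event as confirmed influenza. Protocol 8.4.2.2.1 speaks of first or only confirmed cases. The supplementary VE estimate at the end of SAP 11.1 treats attack rates as binomial, which requires at most one event per subject; that is a natural purpose for the sentence. The documents also use ILI loosely for the counted case, for example in the last column of SAP Table 5-1 and in the SAP 5 remark on early termination. An analyst would have to override the endpoint and the model to lose a case.

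Most of this stands, and one confirmed case per subject is the likely intent. It does not settle the matter. The usage is inconsistent: SAP 5, 8.5 and 14.1 elsewhere add the word confirmed, and this sentence does not. No passage defines the first ILI episode as the first confirmed one.

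Two further readings go too far:

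- A reader might take the censoring sentence as a second error. Under the model in SAP 11.1, a subject with only unconfirmed ILI is right-censored anyway, so this is a matter of aligning the wording.
- A reader might infer that an ILI before the window also uses up the subject's event. SAP 11.1 and 7.3 limit evaluation to the period after the last vaccination plus 14 days, so the documents do not support extending the point that far.

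**Conclusion.** The conflict in wording is real and sits in the confirmatory event rule, so it should be corrected before unblinding. The consequence is conditional: cases are lost only if the sentence is applied literally. For assumed losses of 5% to 30%, co-primary power would then be 89.3% to 78.5% instead of 90.7%, provided that analysed events fall short of a monitored count of 381. If monitoring applied the same first-ILI rule, the trial would continue to 381 countable events, at the price of time or enrolment.

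A reader might conclude that the primary analysis will lose cases, that it will have fewer than 381 events, or that VE will be biased. The documents support none of these. The intent is probably benign, the three-season condition may carry the count past 381, and no bias is expected when other ILI is independent of influenza and equally frequent in both arms. The actual loss cannot be derived, because no rate of non-influenza ILI is given.

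**What to change.** Replace the sentence in SAP 11.1 with:

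> The primary analysis counts at most one event per subject: the first RT-PCR- or culture-confirmed influenza with onset in the efficacy window defined in Section 2.1.2. An ILI episode not confirmed as influenza (test-negative, not swabbed, or without a result) neither ends follow-up nor prevents a later confirmed case from being counted.

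The reference to Section 2.1.2 brings in both ends of the window. Unswabbed and untested episodes are named because swabs are not taken more than 6 days after onset (Protocol 7.2) and because SAP 8.2.3 foresees swabs without an RT-PCR record.

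In both copies of the censoring sentence in SAP 11.1, refer to subjects without confirmed influenza instead of subjects without ILI. The same edit in Protocol 8.4.2.2.4 is optional alignment.

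How confirmed influenza before the window is handled is a separate question for the sponsor to answer in one sentence; the text above is not meant to decide it.

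The cost is three wording edits in the SAP and one optional edit in the protocol. No new data are needed, because a swab is already planned for each protocol-defined ILI. The targets of 381 and 298 events stay as they are.
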